8.1.2 Serious Adverse Event

The following criteria qualify an AE as an SAE:

Death: An event resulting in death (including a fetal death).

In the opinion of the investigator, an event that would have Life-threatening:

> resulted in immediate death if medical intervention had not been undertaken. This does not include an event that would have been fatal if it had occurred in a more severe form.

Hospitalization: An event resulting in inpatient admission of the subject to

> the hospital. (Note: Inpatient hospitalization refers to any inpatient admission, regardless of length of stay). Visits to the emergency room or outpatient facility do not constitute

hospitalization for the purpose of the definition.

Prolongation of An event that prolongs the subject's stay in the

hospital. By definition, this is a different event from Hospitalization:

the event that resulted in the hospitalization.

Congenital Abnormality: An abnormality detected at or after birth in the offspring of a study subject.

Persistent or Significant An event that substantially interferes with the subject's Disability/Incapacity: daily activities of living. This category is not intended to

include events of relatively minor medical significance

such as minor trauma, diarrhea, nausea, etc.

Important Medical Event: A medically important event or reaction that may not be

immediately life-threatening or result in death or hospitalization but may jeopardize the subject or requires intervention to prevent one of the other outcomes listed above. Examples of such events include intensive treatment in an emergency room or at home for allergic bronchospasm, blood dyscrasias or convulsions that do not result in hospitalization, or development of drug

dependence or drug abuse.

8.1.3 Adverse Drug Reaction

All noxious and unintended responses to a medicinal product that are related to any dose should be considered adverse drug reactions (ADR). The phrase "responses to a medicinal product" means that a causal relationship between a medicinal product and an AE is at least a reasonable possibility (i.e., the relationship cannot be ruled out).

8.1.4 Unexpected Adverse Drug Reaction

An unexpected ADR is an adverse reaction for which the nature or severity is not consistent with the applicable product information.

8.1.5 Suspected Unexpected Serious Adverse Reaction

An AE suspected to have a causal relationship to an investigational or marketed drug and meeting criteria for seriousness and unexpectedness. Suspected unexpected serious adverse reactions (SUSARs) are also reportable for active comparator products, placebo, or the clinical study protocol itself (i.e., events due to study procedures).

8.1.6 Unanticipated Adverse Device Effect

An unanticipated adverse device effect (UADE) means any serious adverse effect on health or safety or any life-threatening problem or death caused by, or associated with, a device, if that effect, problem, or death was not previously identified in nature, severity, or degree of incidence in the investigational plan or application (including a supplementary plan or application), or any other unanticipated serious problem associated with a device that relates to the rights, safety, or welfare of subjects.

8.1.7 Adverse Events Related to Hemodialysis Therapy (Anticipated Adverse Events)

The following are common adverse reactions (signs, symptoms and diagnoses) that have been reported related to HD therapy: hypotension; hypertension; muscle cramps; nausea; vomiting; headache; chest pain; back pain; itching; fever; chills; disequilibrium syndrome; hypersensitivity (allergic) reactions including asthmatic reactions, respiratory arrest, pruritus, urticaria, erythema, and peripheral and facial edema; hypovolemia; hypervolemia; cardiac arrhythmia; cardiac tamponade; intracranial bleeding; seizures; hemolysis; air embolism including micro-air embolism; blood loss; infection; access-related problems including infiltration;

abdominal pain; fluid overload; hematuria; bleeding; and electrolyte imbalance.¹⁵⁻¹⁸ Definitions of these adverse reactions are provided in Appendix 4.

8.1.8 Microbiological-Associated Adverse Events

If a failed water sample is accompanied by AEs such as fever, rigors or sepsis within 4 hours after a HD treatment, the event will be considered a microbiological-associated AE(s). The events will be documented on the AE eCRF; the positive culture results will be documented on a Product Issue Form.

A failed dialysate sample from a device actively treating a subject will always be considered a microbiological-associated AE, regardless of whether accompanied by symptoms. The events will be documented on an AE eCRF; the positive culture results will be documented on a Product Issue Form.

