When performed in the home setting, the absence of immediate access to medical personnel and technical support places greater responsibility on patients and care partners for the management of the inherent risks associated with performing HD. Due to the timing

(overnight) and duration of treatment, these risks may be greater with nocturnal HD but can be mitigated with innovative safety features within HD devices, appropriate patient support and training, and provision of tools to allow remote monitoring of patient treatments by their healthcare professionals.

For logistical (patient and provider) and economic reasons, short daily HD or frequent nocturnal HD is typically performed in the home environment. Analysis of the US Renal Data System data from 2017 showed that despite the potential clinical and humanistic benefits, the delivery of HD in the home environment in the US is limited to ~7000 patients, or just 1.4% of all dialysis patients. Only a small minority of these patients perform home nocturnal HD.

The present study will evaluate the safety of a home-based HD system used for hemodialysis in nocturnal home settings.

DEKA Protocol DKPL-00057-001 (Clinical Evaluation of The HemoCareTM Hemodialysis System for Home Nocturnal Hemodialysis) is currently enrolling up to 70 subjects who are receiving a regimen of HD at least 3 times every seven days in order to achieve approximately 30 subjects entering the Unassisted Home Evaluable Period. Eligible subjects and their care partners enter an In-Facility Introduction Period where training is conducted. Upon completion of training, subjects and their care partner enter a transition period (Transition Period A), followed by the Assisted Evaluable Period. During the Assisted Evaluable Period, subjects receive extended duration HD treatments (5-10 hours per treatment) administered by a Medical Professional prescribed to occur every other day, preferably in a home setting. After successful completion of the Assisted Evaluable Period, subjects enter a second transition period (Transition Period B) in the home setting. This will be followed by the Unassisted Home Evaluable Period where the subject and/or care partner will perform each treatment in the subject's home. Subjects will receive a minimum of 34 HD treatments (5-10 hours per treatment) in each Evaluable Period with treatments prescribed to occur every other day.

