4 INVESTIGATIONAL PLAN

4.1 Overall Study Design and Plan

This is an open-label rollover study for subjects and care partners who have completed DEKA Protocol DKPL-00057-001. Enrolled subjects will receive home HD per clinician prescription. Subjects will be seen in the clinic for monthly labs which, at a minimum, would include: hemoglobin, BUN, creatinine, electrolytes, calcium, and phosphorus. Water sampling (AAMI Analysis) will be done once per year or as required by site policy or local regulations, ultrapure (water or dialysate) sampling will be quarterly or as required by site policy or local regulations, and venous line infusion quality dialysate sampling will be done monthly.

See Appendix 1, Study Events Table.

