8 ADVERSE EVENT REPORTING

8.1 Adverse Events and Serious Adverse Events

An AE is any untoward medical occurrence in a subject administered a study product and which does not necessarily have a causal relationship with the treatment or study product.

An AE can therefore be any unfavorable and unintended sign (including an abnormal laboratory function), symptom (e.g., rash, pain, discomfort, fever, dizziness, etc.), disease (e.g., bacteremia, pancreatitis, etc.) or outcome of death temporally associated with the use of the study product, whether or not the event is considered to have a causal relationship with the study product.

Laboratory and vital sign abnormalities qualify as AEs if medical intervention is required to treat or address the abnormality, if the subject must be discontinued from the study due to the abnormality, or if the value exceeds specific limits defined by the protocol as qualifying it as an AE (see Appendix 4).

An elective procedure/surgery that occurs during the course of a study but is being performed for a documented pre-existing condition and was pre-planned prior to study entry will not qualify as an AE. If, however, the pre-existing condition unexpectedly deteriorates during the study requiring the procedure/surgery to be performed earlier than planned, the condition for which the procedure/surgery is being performed will qualify as an AE.

Adverse events will be collected starting from the time the subject signs the ICF until the end of the study. If an AE occurs, a full description of the event should be recorded including the date of onset, severity, time course, description, actions taken, and causal relationship of the AE to the study product(s). Investigators should review and reference the Causality definitions below when determining relationship of the AE to the study product. The Investigators may also discuss the event(s) with the Medical Monitor, but the Investigator must make, document and report the relationship for every AE. All AEs must be documented in source documents and on the eCRFs, no matter how common they are for a particular subject and regardless of the causality assigned by the Investigator.

All AEs and SAEs, regardless of relatedness, should be actively solicited and recorded.

Additionally, any AE voluntarily reported by the subject should be recorded and verified by the Investigator or designee on the appropriate source documents and eCRF pages.

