8.1.1 Definitions of Adverse Event Terms

Study Product: For this protocol, the term "study product" is synonymous with IP.

Date of Onset: The date that the signs and symptoms of the AE began.

Severity: Severity will be assessed for each AE and defined using the following criteria:

Mild – Asymptomatic. A transient discomfort and does not interfere in a significant manner with the subject's normal functioning level. The AE resolves spontaneously or may require minimal therapeutic intervention.

Moderate – Produces limited impairment of daily function and can require minimal, local or non-invasive therapeutic intervention, but produces no sequelae.

Severe or Medically Significant – Requires hospitalization or prolonged hospitalization. Results in a marked impairment of function and can lead to temporary inability to resume usual life pattern. The AE produces sequelae requiring (prolonged) therapeutic intervention.

Causality:

Causality Assessment – A determination is made bythe Investigator and sponsor as to whether there is a reasonable possibility that the device or drug is etiologically related to/associated with the AE. Causality assessment includes, for example, assessment of temporal relationships, association (or lack of association) with underlying disease, treatment association (or lack of association), presence (or absence) of a more likely cause, and physiologic plausibility. Categories for causality assessment are "probably associated," "possibly associated," "unlikely associated" and "not associated."

Related: An AE follows a strong temporal relationship to the device or drug, and another etiology is unlikely or significantly less likely.

Possibly Related: An AE follows a reasonable temporal relationship to the device or drug, and an alternative etiology is equally or less likely compared to the potential relationship to the device or drug.

Unlikely Related: An AE has little or no temporal relationship to the device or drug and/or a more likely alternative etiology exists.

Not Related: An AE that is due to underlying or concurrent illness, complications, concurrent treatments or effect of another concurrent drug/therapy and is not associated to the device or drug (i.e., does not follow a reasonable temporal relationship to the use of the device or drug, or has a much more likely alternative etiology).

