11.5 Primary Endpoints

11.5.1 Primary Safety Endpoint(s)

Safety endpoints will summarize the number of subjects having AE and the number of AE: Number and proportion of subjects having AE and SAE, Number of AE and SAE, and rate of AE/100-Treatment and SAE/100-Treatment.

All the above indicator will be broken down by SOC, PT, Anticipated/unanticipated, and Related/un-related.

Safety will be assessed by evaluating AEs. In addition, monthly laboratory draws will be assessed.

Adverse events will be mapped to a primary MedDRA SOC and PT. Anticipated AEs and SAEs (includes all AEs related to dialysis as identified in Section 8.1.7) and unanticipated AEs and SAEs (excludes all AEs related to dialysis identified in Section 8.1.7) will be summarized during by SOC and PT. In addition, all device-related AEs and SAEs will be summarized by SOC and PT.

An overview of the total number of AEs and SAEs (anticipated, unanticipated, and device- related) will be provided. In addition, an overview will be provided of the total number of subjects having at least one:

[figure not shown]
- a. anticipated AE
- b. anticipated SAE
- c. unanticipated AE
- d. unanticipated SAE
- e. device-related AE
- f. device-related SAE (UADE)

The proportion of subjects having at least one AE within each of these six AE subgroups will be summarized descriptively.

Furthermore, the proportion of subjects having AEs within each of these six AE subgroups will be summarized by SOC, PT and severity (mild, moderate or severe) for the most severe rating of each AE per subject. And, the AE rate per 100 HemoCareTM Hemodialysis System treatments will be calculated.

Descriptive summary statistics will be provided for the visit values and change from DEKA Protocol DKPL-00057-001 baseline in monthly laboratory draws.

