Seizures: Convulsions or other clinically detectable events caused by a sudden discharge of electrical activity in the brain. New onset seizures confirmed by electroencephalogram (EEG).

Hemolysis: For hemodialysis subjects it is the destruction of red blood cells (RBCs) because of their exposure to: 1. Overheated dialysis solution, 2. Hypotonic dialysis solution (insufficient concentrate-to-water ratio), and 3. Dialysis solution contaminated with formaldehyde, bleach, chloramines (from city water supply), copper (from copper piping), fluoride, nitrates (from water supply), zinc, and hydrogen peroxide. Blood line obstruction/narrowing may also be a cause. Symptoms are non-specific and may include nausea, vomiting, chest pain, abdominal pain, shortness of breath and hypotension. Laboratory confirmation of hemolysis as increased in free plasma hemoglobin level and increased serum lactate dehydrogenase.

Air embolism/Micro-air embolism: Obstruction of a blood vessel caused by an air bubble. For hemodialysis subjects, this can occur when air enters through an arterial needle, prepump arterial tubing segment and an inadvertently opened end of a central venous catheter. Micro-air bubbles can become trapped in the hollow fibers of the dialyzer reducing efficiency of dialysis and can also lead to clotting of the circuit.

Blood loss: Loss of blood during a hemodialysis treatment usually created by clotting or disconnect/leak within the extracorporeal circuit.

Infection: A disease caused by microorganisms, especially those that release toxins or invade body tissues. The diagnosis confirmed by bacteriological culture of the infected site as in an access or blood cultures for systemic infection.

Access related problems:

Infiltration: Dysfunction of the subject's vascular access which includes dislocation of the vascular access device from the vessel into the surrounding tissues.

Thrombosis: Occlusion of the lumen of the vascular access due to clots leading to low blood flow. This is confirmed by angiography or surgery.

Stenosis: Narrowing of the vessel lumen confirmed by vascular imaging such as duplex ultrasound.

Aneurysm: Progressive enlargement and weakening of the fistula wall which may lead to bleeding.

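### Symptom-free failed dialysate samples count by default as unanticipated AEs in the primary safety endpoint and should be shown separately

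*Combined protocol and SAP*

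**What the plan says.** Section 8.1.8 has two rules for failed samples.

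- **Dialysate:** "A failed dialysate sample from a device actively treating a subject will always be considered a microbiological-associated AE, regardless of whether accompanied by symptoms". The event goes on an AE eCRF and the positive culture on a Product Issue Form.
- **Water:** the rule is conditional. It begins "If a failed water sample is accompanied by AEs such as fever, rigors or sepsis" and limits the symptoms to the four hours following dialysis.

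The general definition in Section 8.1 reads: "An AE is any untoward medical occurrence in a subject administered a study product".

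Section 8.1.7 lists the reactions that count as anticipated and refers to Appendix 4 for their definitions. Section 11.5.1, the primary safety endpoint, splits AEs into anticipated events and "unanticipated AEs and SAEs (excludes all AEs related to dialysis identified in Section 8.1.7". It reports numbers of events, proportions of subjects and rates per 100 treatments. It adds overview lines for anticipated, unanticipated and device-related events and a breakdown by SOC, PT and relatedness. The visible text of 11.5.1 makes no separate provision for the events of Section 8.1.8.

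On sampling frequency, Section 4.1 says that "venous line infusion quality dialysate sampling will be done monthly".

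**The concern.** The primary endpoint is meant to describe what happens to subjects on the system. Under Section 8.1.8 a culture result from the dialysate becomes a subject's AE even when no finding in that subject is reported. By the definitions it then falls into the unanticipated group, although the protocol itself foresees this type of event and has a rule for it.

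The difficulty is not the lack of symptoms. Section 8.1 accepts abnormal laboratory findings as AEs, and the Mild grade in Section 8.1.1 begins "Asymptomatic. A transient discomfort and does not interfere in a significant manner". The difficulty is that the finding lies in the fluid and not in the subject.

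At stake is how the overview can be read. A reader of the unanticipated or device-related line could not tell events in subjects from failed fluid tests.

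**Working it through.** **Figures in the plan.** There is none to reproduce. Section 11.2 says that the sample size does not rest on a power calculation, and no failure rate is given. The first check is therefore one of classification.

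**Classification of a symptom-free failed dialysate sample**

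1. Is it an AE? Yes, explicitly, under Section 8.1.8.
2. Is it on the Section 8.1.7 list? No. That list holds signs, symptoms and diagnoses; a failed sample is not among them.
3. Could it count as the listed term infection? No. Appendix 4 defines infection as a disease and adds: "The diagnosis confirmed by bacteriological culture of the infected site as in an access or blood cultures for systemic infection". A dialysate culture is neither of these.
4. Which group does it enter under Section 11.5.1? Unanticipated, because that group is everything outside the 8.1.7 list. It also enters the device-related group if the causality assessment says so.

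The label in step 4 is not written in Section 8.1.8. It follows from 8.1.7 and 11.5.1 read together.

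**Size without an assumed failure rate**

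Inputs: Section 2.1 says that the parent study enrols "in order to achieve approximately 30 subjects entering the Unassisted Home Evaluable Period", and Section 11.2 plans to enrol its completers. N = 20 to 30 is an assumption based on this. The frequency of 3 to 6 treatments per week is also an assumption; it is the range that Section 2.1 gives for extended therapies.

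- Shift in the proportion per subject whose only unanticipated AE is such a failure = 100/N: 3.3 points (N = 30), 4.0 (N = 25), 5.0 (N = 20).
- Treatments per subject-year = weekly number × 365.25/7: 156.5 at 3 per week, 313.1 at 6 per week.
- Shift in the yearly rate per failure = 100/(N × treatments): 100/(20 × 156.5) = 0.032; 100/(30 × 313.1) = 0.011 per 100 treatments.

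**Illustration with an assumed failure rate**

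Let f be the probability that a monthly sample fails without symptoms, taken as 1% to 5% (assumption), over 12 samples. Let ρ be the within-subject correlation (assumption). The share of subjects with at least one failure is 1 − (1 − f)^12 for ρ = 0. For 0 < ρ < 1 it is the beta-binomial value 1 − Π(b + i)/(a + b + i), i = 0 to 11, with a = f(1 − ρ)/ρ and b = (1 − f)(1 − ρ)/ρ. At ρ = 1 it equals f.

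| ρ | f = 1% | f = 5% |
|---|---|---|
| 0 | 11.4% | 46.0% |
| 0.1 | 7.6% | 33.2% |
| 0.3 | 4.6% | 21.2% |
| 0.5 | 3.1% | 14.5% |
| 1 | 1.0% | 5.0% |

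Repeat samples share a device and a water source, so independence is the upper end.

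These are subjects with any such failure. The rise in the unanticipated proportion is smaller, because subjects who already have another unanticipated AE do not move it. If half already do, independently of sample failure (assumption), the rise is half of the table: 5.7 to 23.0 points at ρ = 0, and 2.3 to 10.6 at ρ = 0.3.

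The added rate per 100 treatments is 1200 × f/treatments per year. At 3 per week it is 0.077 to 0.383, and at 6 per week 0.038 to 0.192.

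**The case against.** The strongest reply is that the rule is intended. Its wording is emphatic, it is confined to a device in use on a subject, and a specific rule may extend a general definition. Stricter handling of dialysate than of water is a cautious safety choice. This stands. A reader might infer that Section 8.1.8 is an error that contradicts Section 8.1; the text does not support that, and the events should go on being collected as AEs.

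Second, the breakdown by PT may already separate these events. This stands in part: the available text does not say which PT is used, and the overview lines pool all events.

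Third, Section 11.1 defers conventions to a SAP, and no separate SAP text is available here. Parts of Sections 7.9.2 and 7.9.3 are also not visible, including what follows confirmation of an out-of-specification result. This limits the point to the visible text of 11.5.1. Removed text may already define a failed sample or separate these events.

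Fourth, the study is descriptive, without a hypothesis test. This stands, and it limits the consequence to how the results are read. Those descriptive summaries are, however, the primary endpoint.

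A reader might also infer that any event around a failed dialysate sample becomes unanticipated. That goes too far. Accompanying fever, chills or infection are Section 8.1.7 terms and would be anticipated.

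**Conclusion.** The point holds for symptom-free failed dialysate samples. Followed as written, the plan counts them as unanticipated AEs, and as device-related ones if so judged, although no occurrence in the subject is required. The gap is in the presentation of the primary endpoint, not in data collection.

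The effect on the proportion can be visible in a small study: 3.3 to 5.0 points per subject concerned, if 20 to 30 subjects enrol. The effect of one failure on the rate is small, at 0.01 to 0.03 per 100 treatments over a year. A reader might take 11% to 46% as the expected rise in the unanticipated proportion. The documents do not support that: it is an upper-end share of subjects with any failure, under assumed failure rates and independence.

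A secondary wording point concerns fever. A reader might infer that Appendix 4 leaves untreated readings at or below 39°C open. It does not. Appendix 4 calls 37 to 39°C normal, Section 8.1.7 sends the definition of fever there, and the vital-sign rule in Section 8.1 excludes such a reading unless it leads to discontinuation. What remains is that Sections 8.1 and 8.1.8 use the word fever without a limit or a direct link to the Appendix 4 entry. That is a matter of clarification and would not be enough alone.

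**What to change.** 1. Leave the Section 8.1.8 recording rule as it is.
2. In Section 11.5.1, and in the SAP, present the overall, unanticipated and device-related AE numbers, proportions and rates with and without symptom-free failed dialysate samples. Report these failures on their own line and name the PT under which they are coded.
3. If failures per sample are wanted, take the number of samples tested from the central laboratory. Section 8.1.8 puts only positive cultures on the Product Issue Form, so that form gives no denominator.
4. Reconcile the use of fever in Sections 8.1 and 8.1.8 with the Appendix 4 entry. No threshold is proposed here.

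The cost is one extra table and some wording. The AE eCRF items listed in Section 8.1.10.1 include no flag for symptom-free status, so it has to be derived by linking the Product Issue Form to the AE records. No additional sampling or subject visits are needed.
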